Inclusion Criteria: Adult patients over the age of 18 years undergoing surgical intervention and inpatient care for one of the following procedures, total hip arthroplasty (THA) (primary, bilateral, and revision) and total knee arthroplasty (TKA) (primary, bilateral, unicompartmental, and revision). Patients must be fluent in the English language.

Exclusion Criteria: Pediatric patients under the age of 18; undergoing more complex hip and knee procedures such as implant resections with or without spacer placement, liner exchange, or THA or unipolar hip arthroplasty related to repair of hip fracture; preexisting physical or cognitive limitations that would hinder their ability to use the mobile application.

Research Activity

Check all that apply and complete the appropriate sections as instructed.

- Drug & Device:** Drugs for which an investigational new drug application is not required. Device for which (i) an investigational device exemption application is not required; or the medical device is

cleared/approved for marketing and being used in accordance with its cleared/approved labeling. (Specify in the Methods section)

2. **Blood:** Collection of blood samples by finger stick, heel stick, ear stick, or venipuncture.
3. **Biological specimens other than blood:** Prospective collection of human biological specimens by noninvasive means that may include: urine, sweat, saliva, buccal scraping, oral/anal/vaginal swab, sputum, hair and nail clippings, etc.
4. **Tests & Procedures:** Collection of data through noninvasive tests and procedures routinely employed in clinical practice that may include: MRI, surface EEG, echo, ultrasound, moderate exercise, muscular strength & flexibility testing, biometrics, cognition testing, eye exam, etc. (Specify in the Methods section)
5. **Data** (medical record, images, or specimens): Research involving use of existing and/or prospectively collected data.
6. **Digital Record:** Collection of electronic data from voice, video, digital, or image recording. (Specify in the Methods section)
7. **Survey, Interview, Focus Group:** Research on individual or group characteristics or behavior, survey, interview, oral history, focus group, program evaluation, etc. (Specify in the Methods section)

NIH has issued a *Certificate of Confidentiality* (COC). *When checked, provide the institution and investigator named on the COC and explain why one was requested.* _____

Biospecimens – Categories 2 and 3

(2) Collection of blood samples. When multiple groups are involved copy and paste the appropriate section below for example repeat section b when drawing blood from children and adults with cancer.

- a. **From healthy, non-pregnant, adult subjects who weigh at least 110 pounds.** For a minimal risk application, the amount of blood drawn from these subjects may not exceed 550ml in an 8-week period and collection may not occur more frequently than 2 times per week.

Volume per blood draw: _____ ml

Frequency of blood draw (e.g. single draw, time(s) per week, per year, etc.) _____

- b. **From other adults and children considering age, weight, and health of subject.** For a minimal risk application, the amount of blood drawn from these subjects may not exceed the lesser of 50 ml or 3 ml per kg in an 8-week period, and collection may not occur more frequently than 2 times per week.

Volume per blood draw: _____ ml

Frequency of blood draw (e.g. single draw, time(s) per week, per year, etc.) _____

(3) Prospective collection of biological specimens other than blood: _____

Review of medical records, images, specimens – Category 5

For review of existing data: provide a date range or an end date for when the data was generated. The end date can be the date this application was submitted to the IRB. Example: *01/01/1999 to 12/31/2015* or all records through *mm/dd/yyyy*.

Date Range:

Check all that apply (data includes medical records, images, specimens).

(5a) Only data that exists before the IRB submission date will be collected.

(5b) The study involves data that exist at the time of IRB submission **and** data that will be generated after IRB submission. Include this activity in the Methods section.

Examples

- The study plans to conduct a retrospective chart review and ask subjects to complete a questionnaire.
- The study plans to include subjects previously diagnosed with a specific disease and add newly diagnosed subjects in the future.

(5c) The study will use data that have been collected under another IRB protocol. Include in the Methods section and enter the IRB number from which the research material will be obtained. *When appropriate, note when subjects have provided consent for future use of their data and/or specimens as described in this protocol.*

Enter one IRB number per line, add more lines as needed

Data Specimens Data & Specimens _____

Data Specimens Data & Specimens _____

Data Specimens Data & Specimens _____

(5d) This study will obtain data generated from other sources. Examples may include receiving data from participating sites or an external collaborator, accessing an external database or registry, etc. Explain the source and how the data will be used in the Methods section.

(6) Video audio recording: *Describe the plan to maintain subject privacy and data confidentiality, transcription, store or destroy, etc.*

HIPAA Identifiers and Protected Health Information (PHI)

Protected health information is medical data that can be linked to the subject directly or through a combination of indirect identifiers.

Recording identifiers (including a code) during the conduct of the study allows you to return to the medical record or data source to delete duplicate subjects, check a missing or questionable entry, add new data points, etc. De-identified data is medical information that has been stripped of all HIPAA identifiers so that it cannot be linked back to the subject. De-identified data is **rarely** used in the conduct of a research study involving a chart review.

Review the list of subject identifiers below and, if applicable, check the box next to each HIPAA identifier being recorded at the time of data collection or abstraction. Identifiers apply to any subject enrolled in the study including Mayo Clinic staff, patients and their relatives and household members.

Internal refers to the subject's identifier that will be recorded at Mayo Clinic by the study staff.

External refers to the subject's identifier that will be shared outside of Mayo Clinic.

Check all that apply:	INTERNAL	EXTERNAL
Name		
Mayo Clinic medical record or patient registration number, lab accession, specimen or radiologic image number	X	
Subject ID, subject code or any other person-specific unique identifying number, characteristic or code that can link the subject to their medical data	X	
Dates: All elements of dates [month, day, and year] directly related to an individual, their birth date, date of death, date of diagnosis, etc.		
Note: Recording a year only is not a unique identifier.		
Social Security number		
Medical device identifiers and serial numbers		
Biometric identifiers, including finger and voice prints, full face photographic images and any comparable images		
Web Universal Resource Locators (URLs), Internet Protocol (IP) address numbers, email address		
Street address, city, county, precinct, zip code, and their equivalent geocodes		
Phone or fax numbers		
Account, member, certificate or professional license numbers, health beneficiary numbers		
Vehicle identifiers and serial numbers, including license plate numbers		
Check 'None' when none of the identifiers listed above will be recorded, maintained, or shared during the conduct of this study. (exempt category 4)	 None	 None

Data Analysis

Power analyses and study endpoints are not required for minimal risk research, pilot or feasibility studies.

No statistical information. *If checked, please explain:*

Power Statement: N/A

Data Analysis Plan

The pre-intervention and post-intervention, paper surveys' will be returned to the researcher for data entry and storage. The collected data will be collated and entered by the researcher into SPSS for data analysis. A detailed code book has been developed to include specific information on the type of variable and the theoretical and operational definitions. Data entry will be double-checked for accuracy by one of the staff trained staff RNs participating in data collection and chart audits. Descriptive statistics will be performed on each study variable. Continuous variables, including pain scores, pain knowledge, and opioid requirements, will be reported using a mean and standard deviation. Categorical variables, including patient characteristics and education engagement, will be reported as frequencies and percent occurrence. The data will be examined for any baseline differences between the groups to identify characteristics that may confound results and require control in the analysis. Data will be examined to assure that it meets the assumptions of normality required for parametric analysis. If data does not meet normality assumptions, nonparametric analyses will be used. This study uses a revised adaption of the Patient Pain Questionnaire (PPQ) survey. For this reason, the reliability and validity of the nine knowledge based questions will be evaluated using Cronbach's alpha and factor analysis.

This study will explore the difference between two types of education delivery methods and the effect on pain scores, participation, knowledge, and opioid requirements. The difference amongst the two study groups will be analyzed using an independent *t*-test. Using the population mean of each group a *t* statistic will be computed. The independent *t*-test was selected because this statistical test is appropriate when there are two groups that are not the same people and are not connected to one another in any other systematic way (Polit, 2010). Additionally, the requirements for the *t*-test fit with the design of the study and variables. The independent variable must be dichotomous nominal level indicating a participants' status in one of the two groups and the dependent variable must maintain the characteristics of interval-scale or ratio (Polit, 2010).

Endpoints

Primary: N/A

Secondary: N/A

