- Determine if there is a significant difference in opioid requirements in the first 48 hours according to the type of education delivery methods.

Background (Include relevant experience, gaps in current knowledge, preliminary data, etc.):

Despite all the available analgesic, modern devices, and nonpharmacological interventions, pain in the acute post-surgical period remains a prominent issue and effective management has remained elusive with significant gaps in care. Early estimates suggest that anywhere from 50% to 75% of surgical patients experience inadequate pain relief (Huang et al., 2001), often due to delayed intervention (Sinatra, Torres, & Bustos, 2002). A National Survey of patients who had undergone non-specific surgical care demonstrated occurrence of acute pain in 80% of patients and moderate to severe pain in approximately 86% of those who experienced acute pain (Apfelbaum, Chen, Mehta, & Gan, 2003). A 2008 study of 1,490 surgical inpatients, 41% of patients reported severe pain in the first 24 hours after surgery (Sommer, de Rijke, van Kellef, et al., 2008). Watt-Watson, Stevens, Garfunkel, Steiner, & Gallop (2001) found severe pain in 86% of coronary artery bypass patient 24 hours after surgery. A chart review revealed that 80% of these patients experiencing severe pain received <16 mg of morphine over the previous 24 hours and two had no analgesia orders in the medical record (Watt-Watson et al., 2001). Ineffective pain management effects recovery, complications, cost (Gordon, Dahl, & Stevenson, 2000), patient satisfaction (Garinella & Cellini, 2013), length of stay (Joshi, Beck, Emerson, et al., 2014), readmissions (ASA, 2012), quality of life (Ersek, 2001), and chronic postsurgical pain (O'Brien, Pergolizzi, van de Laar, et al, 2103; Barrington, Halaszynski, & Sinatra, 2014).

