
Study Design and Methods

Methods: *Describe, in detail, the research activities that will be conducted under this protocol:*

Variables

The independent variable is the type of patient education deliverable given to the two study arms, group A (experimental group, real-time, interactive, mobile education system) and group B (control group, standard of care). The dependent variables are 1) patient knowledge, 2) patient perceived participation in pain management, 3) high and low pain scores, and 4) total opioid consumption. A simple table of the independent, dependent, and additional variables are presented in Appendix B. A detailed accounting of all data points including variable type, theoretical definitions, and operational definitions can be found in the detailed code book.

Method

Design

This prospective study has been designed as quasi-experimental study. This study design was selected for several reasons. This study seeks to explore both a treatment and control group in efforts to compare outcomes which are dependent on the type of intervention. To control for fidelity of the intervention and avoid cross over, behavior changes from nurses providing the intervention, the intervention the patient receives will be determined by the location they are bedded in hospital. Orthopedic TJA patients are assigned at random and based on bed availability to one of two patient care units. One of the two patient care units will offer standard education the other unit will offer the mobile, iPad based education. The patient care unit to offer the mobile, iPad based education will be selected at random. This study design will help minimize will reduce the risk of selection bias, increase fidelity of the intervention, and increases the probability that the differences demonstrated between the study groups will be attributed to the actual intervention under study.

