Enrollment into the study is completely voluntary. Participating in this study poses minimal risk to the participants; all patients will receive the necessary education to meet their care needs and the minimum standard of practice. The potential for risk is that the mode of information/education delivery does not meet the patients' needs and the risk of low acceptance of technology use. In this case, patients in the study arm would be removed from the study and would receive standard education. Pain management in both arms will remain the same; no changes will be made to the process for treating pain using either non-pharmacologic or pharmacologic interventions. Medication orders, medication administration, and pain treatment plans will not be affected by participation in study. As care is today, pain management will be customized to meet the needs of the individual patient.

Oral consent will be obtained, documented, and maintained as part of the research records. No identifiable patient information will be maintained. The only identifiable information collected will be the patients' clinic number. It will be used for tracking purposes only until the data collection process is complete. When the chart audit is complete, the clinic numbers will be removed from the data set and only the predesignated subject number will be used and maintained. At the start of the study the patient will be asked to complete the HIPAA Authorization to Use and Disclose Protected Health Information. The researcher will remain blinded to the type of education delivery that the patient will receive until after enrolment and bed assignment. This will prevent potential bias with inadvertently assigning patients to groups based on characteristics, like age.

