Pain outcomes. The Revised American Pain Society Patient Outcome Questionnaire (APS-POQ-R) will be used to evaluate the patients' perception of their pain management experience and outcomes (Appendix E). The APS-POQ-R is a 23-item, two-page questionnaire measuring five subscales of the patient experience and one aspect measuring non-pharmacologic management. These 6 aspects include (1) pain severity and relief; (2) impact of pain on activity, sleep, and negative emotions; (3) side effects of treatment; (4) helpfulness of information about pain treatment; (5) ability to participate in pain treatment decisions; and (6) use of nonpharmacological strategies (Gordon, Polomano, Pellino et al., 2010). There are 14 symptom-based questions to indicate symptom severity using a ten-point scale (0-10). The higher the score, the more severe the symptom experience. Two additional symptom-based questions explore severity of pain over time and pain relief using a ten-point scale with a range of 0% to 100%. For pain severity over time, a higher score indicates a higher incidence of severe pain in 24 hours. For pain relief, a higher score indicates a more positive response to pain relief. These data points will help determine the effectiveness of the intervention on pain outcomes (pain scores). Three questions are associated with the pain education experience. Using a ten-point scale (0-10), the higher response scores indicate a more positive experience rating. Pain experience here is assessed by

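### Treatment side effects are collected on the APS-POQ-R but have no planned between-arm comparison, so an opioid difference can be read against pain but not against tolerability

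*Combined protocol and SAP*

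**What the plan says.** The outcomes are fixed in two places. Study Design and Methods, Variables, states: "The dependent variables are 1) patient knowledge, 2) patient perceived participation in pain management, 3) high and low pain scores, and 4) total opioid consumption". The Data Analysis Plan says the study explores "the effect on pain scores, participation, knowledge, and opioid requirements", and continues: "The difference amongst the two study groups will be analyzed using an independent *t*-test".

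The fourth aim, under Research Question and Aims, is: "Determine if there is a significant difference in opioid requirements in the first 48 hours according to the type of education delivery methods". No direction is given. The general hypothesis speaks of improved pain outcomes and higher participation, and does not say whether more or less opioid would be an improvement. Opioid totals come from the medication administration record (Instruments, Chart audits).

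The APS-POQ-R is described under Instruments, Pain outcomes. Its aspects begin with "1) pain severity and relief; (2) impact of pain on activity, sleep, and negative emotions" and go on to "3) side effects of treatment; (4) helpfulness of information about pain treatment". The same section gives Cronbach alphas for five subscales. The adverse-effects subscale has the lowest, 0.63. The questionnaire is completed at discharge (Data Collection Procedure).

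In the aims, side effects appear only as something patients should know about, not as something they experience.

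Recruitment and Consent adds: "Medication orders, medication administration, and pain treatment plans will not be affected by participation in study".

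**The concern.** The study tests whether education changes how much opioid patients receive, but does not fix which change is favourable. The Background can be used for either. It describes severe postoperative pain with little morphine given, which would make higher use look like better treatment. It also raises misuse and adverse-effect concerns in opioid-naive patients, which would make lower use look better.

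Pain scores and side effects are the two results that help a reader interpret an opioid difference. Only pain scores are on the outcome lists. Followed as written, the trial could report higher opioid use with lower pain as an improvement, with no planned look at whether side effects rose. It could equally report lower use at equal pain without showing whether tolerability improved, which would be the main gain to the patient.

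The protocol's own rationale points the same way. The Background defines effective pain management as a balance of relief and safety, and the Significance section counts adverse effects among the outcomes on which evidence is limited.

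**Working it through.** **1. Where side effects appear.**

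| Place | Side effects included? |
|---|---|
| Aims | Knowledge of them only |
| Variables (four dependent variables) | No |
| Instruments, Pain outcomes (APS-POQ-R) | Yes: aspect 3 of 6, with its own subscale |
| Data Collection Procedure | Yes: the form is completed at discharge |
| Data Analysis Plan, descriptive statistics | Only through the general line covering each study variable |
| Data Analysis Plan, between-arm comparison | No |

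The data are collected, but no comparison between arms is named.

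**2. The plan's own sample size.** Inputs from Sample Size: d = 0.50, power 80%, alpha 0.05. Sidedness is not stated; two-sided is taken.

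- Normal approximation: n = 2 × (1.960 + 0.842)² / 0.50² = 62.8, so 63 per arm.
- Noncentral t: 63.77, so 64 per arm, with power 80.1% at 64.

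The stated 64 per arm (128 in total) is reproduced. A one-sided calculation gives 50 and does not match. The point disputes no figure in the plan.

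**3. Precision for the side-effect difference.** In SD units, the 95% CI half-width is t(0.975, 2n − 2) × √(2/n).

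- 64 per arm: 1.979 × √(2/64) = 1.979 × 0.1768 = **0.35 SD**.
- 62 per arm (the total of 124 given under Setting): 1.980 × √(2/62) = 1.980 × 0.1796 = 0.36 SD.
- 50 per arm (an assumption, to show the effect of incomplete forms): 1.984 × √(2/50) = 1.984 × 0.2 = 0.40 SD.

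**4. What 0.35 SD does and does not mean.** If the arms are truly equal, the observed difference falls below zero half the time. The upper confidence limit is therefore below 0.35 SD only about half the time. To exclude a worsening with 80% probability, the margin must be about (1.979 + 0.842) × 0.1768 = 0.50 SD.

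**5. Why an estimate and not a fifth test.** With tests at 0.05, assumed independent, the chance of at least one false positive is:

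- four tests: 1 − 0.95⁴ = 18.5%;
- five tests: 1 − 0.95⁵ = 22.6%.

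With a Bonferroni correction over five tests, 64 per arm gives 58.5% power at d = 0.50, and 80% power needs about 96 per arm. An interval without a test avoids both costs and leaves 64 per arm unchanged.

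**The case against.** **Pain is compared.** A reader might infer that an opioid difference could not be read as benefit or harm at all. The documents do not support that. Pain scores are a dependent variable, so lower use at equal pain can be told apart from lower use at worse pain. Only the tolerability side is missing.

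**Side effects may be reported anyway.** A reader might infer that the trial would say nothing about them. That also goes too far. Descriptive statistics are planned for each study variable. The stated use of the symptom items is broad, and the first aim, on pain experience, could be read to include them. Appendix B and the code book are not in the supplied text and may list them as additional variables. What stands is that Variables and the Data Analysis Plan name the outcomes to be compared, and side effects are not among them.

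**The medication statement has a natural reading.** Taken alone, "Medication orders, medication administration, and pain treatment plans will not be affected by participation in study" seems to rule out the effect that the opioid aim tests. In context it follows a sentence saying the process for treating pain is unchanged, and precedes one saying care is customised to the patient. It can be read as saying that the protocol directs no change in treatment, which is compatible with patients asking for more or less. It is loose wording, not a firm contradiction, and it does not cause the gap in the outcomes.

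**The Background does not say education raises adverse effects.** It links that risk to lack of knowledge in opioid-naive patients and expects education to help. The case here does not need the stronger claim.

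**Minimal-risk template and modest reliability.** The template does not require endpoints for minimal-risk research, and alpha 0.63 is the lowest of the subscales. Both argue against a formal test, but not against reporting a difference with its interval.

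**Conclusion.** The point holds in limited form. Side effects are collected but not named for comparison between arms, and the opioid aim has no stated direction. An opioid difference could therefore be interpreted against pain but not against tolerability.

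The comparison would have a 95% CI half-width of about 0.35 SD. This assumes that all 128 patients have complete forms and that their responses are independent. Both assumptions are favourable. Recruitment and Consent removes study-arm patients for whom the technology does not work. Each arm is a single care unit, so any difference between the units is not in the interval. A reader might take 0.35 SD as the worsening the trial could rule out; with truly equal arms it would do so only about half the time.

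The conclusion on the omission rests on the text, not on any calculation. Appendix B or the code book could show that side effects are a listed variable, but the two outcome lists would still need the addition.

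**What to change.** 1. In Variables and in the Data Analysis Plan, name the APS-POQ-R adverse-effects subscale at discharge as a safety (balancing) outcome. Report it as a between-arm difference with a 95% confidence interval and no formal test.
2. Present that difference beside the opioid and pain-severity differences, so that the three are read together. A rule for when an opioid difference may be called an improvement is optional and is not needed for this fix.
3. As a lesser point, reconcile the medication-administration sentence in Recruitment and Consent with the opioid aim. The sponsor should state whether it means that the protocol directs no change in treatment or that no change in administration is expected.

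Cost: a few sentences of protocol wording and one more estimate from data already collected, with no change to the sample size. The downside is an additional outcome on a subscale with alpha 0.63, so a small or null difference should be read with caution.

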Study participants will be assigned into one of two study arms, intervention or control, based on random assignment to the two designated units. At the time of consent, patients will be informed that there are two study arms and that some subjects will receive enhanced pain management education; however, subjects will not explicitly be informed if they are in the intervention or control arm of the study. Participants who have verbally consented will receive a HIPAA authorization form accompanied by a letter reminding them of the study and their consent to participate at the time of the preoperative visit. This typically occurs one to two days before surgery. Participants will be asked to sign the HIPAA authorization form and return the clinical staff. Participants will be provided an extra copy for their records. No Patient data will be collected prior to this. Once HIPAA has been signed participants will complete the intake survey provided with the packet of information.

Researchers are blinded to the study arm the participant was enrolled in until after consent has been obtained, the patient is enrolled in the study, and has been admitted to the hospital and assigned a bed. Once enrolled and consented, bed control will be notified to assign the patient(s) to one of the two designated patient care units with no specific direction offered on which unit the patient(s) should be assigned to. The only direction provided will be to split the patients evenly between the two units. Only ten study arm participants may be enrolled and active at one time. This is limited based on the number of available iPad devices for the purposes of this study.

Study Population

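### Each arm is a single nursing unit, so the education effect cannot be separated from other unit differences; the attribution claim, the patient-level random wording and the Limitations section do not reflect this

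*Combined protocol and SAP*

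**What the plan says.** The Design section labels the study openly: "This prospective study has been designed as quasi-experimental study". It gives a reason for delivering the education by unit, namely to protect fidelity and avoid crossover between nurses, and states that "the intervention the patient receives will be determined by the location they are bedded in hospital". One of two orthopedic units offers the iPad programme and the other offers standard education. One explicit random step is described: "The patient care unit to offer the mobile, iPad based education will be selected at random".

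Patient placement is described in two ways. Design says "Orthopedic TJA patients are assigned at random and based on bed availability to one of two patient care units", and then that participants enter an arm "based on random assignment to the two designated units". The process given is that bed control is told to place enrolled patients on one of the two units "with no specific direction offered on which unit the patient(s) should be assigned to", and "The only direction provided will be to split the patients evenly between the two units". At most ten iPad-arm patients may be active at once. Researchers do not know the arm until the patient has consented, enrolled, been admitted and been given a bed (Design; Recruitment and Consent).

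Design concludes that this approach reduces selection bias, improves fidelity and "increases the probability that the differences demonstrated between the study groups will be attributed to the actual intervention under study". Limitations mentions the two units only because nurses may float between them. The Data Analysis Plan has a check for baseline differences between groups and a patient-level independent t-test.

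**The concern.** With one unit per arm, anything else that differs between the units (staffing, habits of pain assessment, how nurses teach and give medication) falls entirely on one side of the comparison. The t-test would report such a difference as an education effect, or let it mask a real one. Its standard error reflects only variation between patients, so nothing in the output would give a warning.

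The text does not prepare the reader for this. The attribution sentence carries no exception for unit-level causes. The confounding that Limitations does name is content with delivery method, not unit with arm. The patient-level random wording suggests a chance mechanism that the documents do not describe. A conclusion written from this plan would credit the education with whatever separates the two units.

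**Working it through.** **1. The plan's own figure.** Sample Size gives d = 0.50, power 80%, alpha 0.05 and 64 per arm. The exact two-sided t solution is 63.77, rounded up to 64. At 64 per arm there are 126 degrees of freedom, the critical value is 1.979 and the noncentrality is 0.5 × √(64/2) = 2.828, which gives power 0.801. The figure reproduces, for patients whose outcomes differ between arms only through the education.

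**2. What can be estimated.** There are two units and two arms. Once arm is in the model, 2 − 2 = 0 degrees of freedom remain for differences between units. No covariate adjustment and no larger sample on the same two units changes this.

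**3. What each safeguard covers.**

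| Safeguard (section) | Addresses | Leaves open |
|---|---|---|
| Random choice of the iPad unit (Design) | Direction of any unit difference | Its presence and size |
| Researcher blinding until bed assignment (Design; Recruitment and Consent) | Selection by researchers | Unit effects; how bed control chooses |
| Pain management unaffected by participation (Recruitment and Consent) | Care changing because of the study | Whether the two units practise alike |
| Both units orthopedic, same hospital (Setting) | Gross dissimilarity | Equality of outcomes |
| Rounds and observations (Management of interventions) | Fidelity | Other unit practices |
| Knowledge pre-test (Limitations) | Change within patients | Effects arising during the stay |
| Baseline comparison (Data Analysis Plan) | Patient characteristics | Unit, which equals arm |

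On the pre-test, the sections disagree about what is measured at baseline. Pain knowledge (Instruments) has both questionnaires completed at the start and at discharge; Data Collection Procedure lists only the knowledge survey at the clinic visit. On either reading the measurement precedes arrival on the unit, the paired test is within patients, and no baseline-adjusted comparison of arms is planned.

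**4. Size, for assumed unit differences.** The documents give none, so a range is shown. With a unit difference b in SD units and no education effect, the noncentrality is b × √32 and the rejection probability is P(|T| > 1.979) with 126 degrees of freedom.

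| Assumed b (SD) | b × √32 | Rejection with no education effect |
|---|---|---|
| 0 | 0 | 5.0% |
| 0.05 | 0.283 | 5.9% |
| 0.10 | 0.566 | 8.7% |
| 0.15 | 0.849 | 13.4% |
| 0.20 | 1.131 | 20.2% |

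At a true d of 0.5 the noncentrality becomes (0.5 ± b) × √32. At b = 0.20, power is 39% if the unit difference opposes the education and 98% if it favours it. Because the iPad unit is picked at random, the average over the two directions is (39 + 98)/2, about 68%.

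**5. Random wording against mechanism.** The only chance step with a described object is the choice of unit. For patients, the documents describe availability, an even split and a cap, with no sequence, list or other random device.

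**The case against.** The strongest reply is that the design is already disclosed. It is called quasi-experimental at the outset, the text says that location determines the education, and the bed-control process is set out in the same section. Unit-level delivery is a reasonable way to avoid contamination. The attribution sentence is comparative: it speaks of raising a probability, and reduced crossover does make attribution easier than mixed delivery on one unit. Researchers cannot steer patients to an arm, which supports the selection-bias clause. Power analyses are also not required by the template for minimal-risk research.

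Most of that stands. The label, the delivery by unit, the 64 per arm and the blinding are not in dispute, and the selection-bias clause should be kept. A reader might go further and infer that the result would pass for a randomised estimate. The documents do not support that, because the label and the mechanism are both printed; the fault is loose use of the word random beside a disclosed process. Nor do the even split and the cap in themselves contradict randomness. The point is only that nothing random is described.

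What the reply does not reach is the aliasing. A quasi-experimental label does not tell the reader that unit and arm coincide, and Limitations, where this belongs, is silent.

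**Conclusion.** The point holds as a matter of what may be concluded. The planned comparison estimates a difference between two units, of which the education is one component, and neither the t-test nor the baseline check can isolate it. The attribution clause is supported for fidelity, crossover and researcher selection, and unsupported for unit-level causes.

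The sizes rest on assumed unit differences of 0.05 to 0.20 SD, 64 per arm and a two-sided 5% test: false rejection of 5.9% to 20.2%. A reader might infer that the units do differ, or that the trial's error rate really is 20%. The documents do not support either. Control group says that verbal teaching depends on the nurse, but that is not evidence of a difference between units. Nor does it follow that the sample size is wrong: 64 per arm is correct on its stated inputs.

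This should be corrected before results are written up; it does not prevent the study from running.

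**What to change.** 1. **Design, attribution sentence.** Keep the clauses on fidelity, crossover and selection bias. Qualify the attribution clause so that it does not extend to differences between the units.
2. **Design and Limitations, carried into the conclusion.** Add: *Results are a difference between two units; the education effect cannot be separated from other differences between the units.*
3. **Design, both statements of patient-level random assignment.** Replace with: *assigned by bed control according to bed availability, with an instruction to split evenly*. Leave the random choice of the iPad unit as written.

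Optionally, state beside the power figure that it assumes equal mean outcomes on the two units under the same education. No separate tipping-point report is needed, because the confidence interval already shows how large a unit difference would bring a significant result to zero.

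The cost is a few sentences. The downside is a less favourable stated conclusion.
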